9.3. Infusion reactions

Since SHR-1210 is a fully humanized monoclonal antibody, it is unlikely to cause infusion reactions, and no prophylactic medication is required before infusion. If an infusion reaction occurs, it should be managed according to the situation by slowing down or interrupting the infusion, providing clinical supportive care, and administering prophylactic medication before subsequent treatments. Acute infusion reactions (including cytokine release syndrome, vascular edema, anaphylactic shock, and allergic reactions, please refer to NCI CTCAE v4.03 criteria) usually occur at the time of infusion or shortly after drug infusion, with symptoms and signs typically disappearing within 24 hours after the infusion is completed. Symptoms and signs include:

Allergic reactions/hypersensitivity reactions (including drug-induced fever), cough, cold intolerance, chills/shivering, dizziness, headache, fatigue (asthenia, somnolence), rash/peeling, pruritus cutaneous/pruritus, joint pain, muscle pain, hypotension or hypertension, nausea, vomiting, sweating (diaphoresis), tachycardia, tumor pain, urticaria (rubella), dyspnea (shortness of breath) or bronchospasm. All grade 3 or 4 infusion reactions should be reported to the sponsor within 24 hours, and if they meet the criteria for SAEs, they should be reported as SAEs. The management of allergic reactions should be based on the medical practice and guidelines of the study site. The

following are treatment recommendations for infusion reactions, for reference.

Table 5 Recommendations for Infusion Reactions Treatment

CTCAE Grade	Clinical Symptoms	Clinical Management	SHR-1210 Treatment
Grade 1 (mild)	Mild transient reaction;	Bedside observation, close monitoring until recovery. (Subsequently, it is recommended to administer prophylactic medication before infusion: at least 30 minutes prior to SHR-1210 administration, diphenhydramine 50 mg or equivalent, and/or acetaminophen 325 ~ 1000 mg)	Continue
Grade 2 (moderate)	Moderate reactions, therapy or infusion interruption indicated but respond promptly to symptomatic treatment (e.g., antihistamines, NSAIDS,	Intravenous infusion of normal saline, diphenhydramine 50 mg IV or equivalent and/or acetaminophen 325 ~ 1000 mg; Bedside observation, close monitoring until recovery. According to clinical needs, corticosteroids or bronchodilators may be considered; The amount of study drug infused should be recorded in the original medical records;	Suspend treatment. When resuming administration after symptom disappearance, use 50% of the initial infusion rate. If no complications occur within 30 minutes, the

	narcotics, bronchodilators, intravenous infusion etc.)	Subsequently, it is recommended to administer prophylactic medication before infusion: at least 30 minutes prior to SHR-1210 administration, diphenhydramine 50 mg or equivalent, and/or acetaminophen 325 ~ 1000 mg. If necessary, hormone cortisol can be used (at a dose equivalent to a 25 mg of hydrocortisone).	infusion rate can be increased to 100% of the original rate. Closely monitor the patient. If symptoms reoccur after resolution, do not administer the current infusion of SHR-1210.
≥ Grade 3 (severe)	Grade 3: severe reactions, which do not respond to therapy and/or dose interruption; or the symptoms reoccur after resolution; sequelae requiring	Grade 3: severe reactions, which do not respond to therapy and/or dose interruption; or the symptoms reoccur after resolution; sequelae requiring	Immediately discontinue infusion of SHR-1210; Permanently discontinue. Initiate intravenous infusion of normal saline. • Bronchodilators: subcutaneous injection of 1:1000 epinephrine solution at a dose of 0.2 ~ 1 mg, or slow intravenous injection of 1:10000 epinephrine solution at a dose of 0.1 ~ 0.25 mg, and/or if necessary, intravenous injection of diphenhydramine 50 mg + methylprednisolone 100 mg or

	hospitalization.	equivalent drug;	
	Grade 4:	• Follow the study site's	
	Life-threatening	guidelines for treating allergic	
	g	reactions; conduct bedside	
		observation, close monitoring	
		until recovery.	

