5.3. Dose modifications

During the study period, dose modifications of the investigational drug can be made based on its toxic side effects, including: dose interruption, dose reduction, modification of administration mode, and dose termination.

Dose interruption is allowed for SHR-1210, with a maximum allowable drug interruption of 12 weeks.

In addition to dose interruption, for subjects whose weight decreases to below 50 kg during the treatment period, the dose of SHR-1210 may be down-titrated to 3 mg/kg q2w, as appropriate.

Dose modifications due to apatinib-related toxicity include: dose interruption, dose reduction, modification of administration mode (first modification: 5 days on treatment and 2 days off; second modification: 7 days on treatment and 7 days off), and dose termination. During the study, after adjusting the administration mode of apatinib, the recovery of dose mode will not be allowed.

During the study, if definite apatinib-related AEs occur, such as hypertension, proteinuria, hand and foot syndrome (HFS), apatinib administration may be down-titrated or interrupted. After toxicity recovery, the original dose, adjusting the administration method, or terminating the dose may be given as appropriate. After discontinuing apatinib, the study subjects may continue to receive SHR-1210 monotherapy.

During the study, if immune-related toxicities occur, such as immune pneumonia,

hepatitis, enteritis, the administration of SHR-1210 and apatinib should be suspended as appropriate. Once the toxicity has recovered to \leq grade 1 or baseline levels (for the increase of laboratory parameters such as ALT/AST and total bilirubin [TBIL]), the medication can be resumed. The administration of SHR-1210 should be resumed first, and after 14 days of observation without significant abnormalities, the administration of apatinib can be initiated and the mode of subsequent administration of apatinib will be adjusted.

During the study, if \geq grade 3 immune pneumonia, \geq grade 3 TBIL increased, grade 4 ALT/AST increased, or other grade 4 immune-related toxic reactions, grade 4 injection reactions occur, or if the immune-related toxicity causes a temporary suspension of SHR-1210 administration for more than 12 weeks and still cannot recover to \leq grade 1 or baseline level, SHR-1210 must be permanently discontinued.

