8.3. Infusion reactions

Investigators need to closely monitor the possible infusion-related and/or allergic reactions, especially acute immune-mediated adverse reactions (including cytokine storms), throughout the study.

In general, prophylaxis is not required before the infusion of SHR-1210. Based on the published literature, allergic reactions/events are most likely to occur within 24 hours of infusion. If this occurs, the infusion should be slowed down or interrupted according to the situation, clinical supportive treatment should be provided, and

prophylactic medication should be administered before future treatments. Possible allergic reactions may manifest as fever, cold intolerance, chills, headache, rash, pruritus, joint pain, hypotension/hypertension, or bronchospasm. All grade 3 or 4 infusion reactions should be reported according to the SAE reporting procedures.

9. Recommendations for Management of Adverse Events

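### Table 5 (protocol section 9.3) gives two different SHR-1210 actions for a grade 2 infusion reaction that resolves and then recurs

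*Protocol*

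**What the plan says.** Section 9.3 sets out infusion-reaction management in Table 5, by grade.

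- **Grade 2 row.** The reaction is described as follows: "Moderate reactions, therapy or infusion interruption indicated but respond promptly to symptomatic treatment". The infusion is suspended, restarted at half the initial rate once symptoms have gone, and returned to the full rate if the next 30 minutes are uneventful. Then: "If symptoms reoccur after resolution, do not administer the current infusion of SHR-1210". For later doses the row adds: "Subsequently, it is recommended to administer prophylactic medication before infusion: at least 30 minutes prior to SHR-1210 administration".
- **Row for grade 3 and above.** The grade 3 description opens with severe reactions that do not respond, and continues: "or the symptoms reoccur after resolution; sequelae requiring" hospitalization. The action is: "Immediately discontinue infusion of SHR-1210; Permanently discontinue".

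Three other places bear on the same event:

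- **Section 5.3** lists the events after which SHR-1210 must be stopped permanently. For this kind of reaction it names only grade 4: "other grade 4 immune-related toxic reactions, grade 4 injection reactions occur".
- **Sections 8.3 and 9.3** attach reporting duties to grades 3 and 4. Section 8.3 says: "All grade 3 or 4 infusion reactions should be reported according to the SAE reporting procedures". Section 9.3 says: "All grade 3 or 4 infusion reactions should be reported to the sponsor within 24 hours", with SAE reporting if the SAE criteria are met.
- **Sections 7.2.1 and 8.1.2** fix CTCAE v4.03 as the severity scale. Section 7.2.1 also plans the rates of dose interruption and dose discontinuation due to AEs.

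**The concern.** The same occurrence, symptoms returning after they had cleared, appears in two rows with different consequences. It is not a remote combination: the grade 2 row itself orders the restart that makes recurrence possible, and then addresses it. Two sub-investigators following the table in good faith could act differently on the same patient, one withholding a single infusion and the other ending SHR-1210.

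That is first a matter of patient management. It also reaches the safety results, because the interruption and discontinuation rates due to AEs are stated secondary safety endpoints and the choice of row decides which of them the event enters.

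**Working it through.** The protocol gives no figure that can be reproduced here, so the check sets the texts side by side for one event: a moderate reaction that clears with symptomatic treatment, is restarted as Table 5 directs, and recurs.

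| Question | Read under grade 2 | Read under grade 3 and above |
|---|---|---|
| Does the row mention recurrence? | Yes, in the SHR-1210 action | Yes, in the description of the grade |
| Action on SHR-1210 | Current infusion not given | Permanent discontinuation |
| Later infusions | Foreseen, with premedication | None |
| Planned AE rate that it enters | Interruption | Discontinuation |
| Grade 3/4 reporting under 8.3 and 9.3 | Not triggered | Triggered |

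1. **Does the event meet both rows?** It meets the grade 2 row by its severity and by that row's explicit recurrence sentence. It meets the grade 3 description because recurrence follows a semicolon and the word or, as an alternative descriptor.
2. **Is there a tie-break?** Neither row refers to the other, and no sentence in 8.3 or 9.3 says which prevails.
3. **Does section 5.3 settle it?** No. It names grade 4 only, so it does not say what grade a recurrent moderate reaction has. It also differs from Table 5, which stops SHR-1210 permanently from grade 3.
4. **Do the severity sections settle it?** For the recorded grade, in principle yes: CTCAE v4.03 is the scale. But the first column of Table 5 is headed CTCAE Grade, so a site could take the table as a statement of that scale. The CTCAE text is not part of the protocol, so it cannot be said here which row departs from it.
5. **Size.** With 30 planned patients (section 10.1), one patient counted differently moves a rate by 1/30 = 3.3 percentage points, assuming all 30 are in the safety set. That holds for any event in any patient and says nothing about how often this one occurs. The protocol gives no recurrence frequency, and section 9.3 calls infusion reactions unlikely.

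**The case against.** The case on the other side has real weight.

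- **The table is advisory.** Section 9.3 bases management on site practice and guidelines and offers Table 5 for reference; the mandatory stopping rule is in 5.3. This stands and lowers the importance of the point. Still, the table is the protocol's only grade-by-grade guide to these reactions, and it should not point two ways.
- **The rows can be read together.** The word severe may govern the whole grade 3 description, leaving a moderate recurrence in grade 2. Or the grade 2 sentence may be only the immediate bedside step, which a permanent stop would also satisfy; the premedication advice covers grade 2 reactions in general and is not tied to recurrence. Both readings are possible, so this is an ambiguity rather than two irreconcilable orders. Neither is stated, and they lead to different actions.
- **The text at hand is damaged.** The grade 3 description is duplicated and the columns are shifted by extraction. That is not a fault of the plan and nothing here rests on it; the operative phrases are legible.

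A reader might infer more: that the recorded grade, the count of events of grade 3 or above and the expedited reporting all turn on the row chosen. The protocol does not support that as a general statement, because severity is tied to CTCAE v4.03 outside the table. It holds only if a site grades from Table 5. A reader might also infer an effect on PFS or duration of response through loss of SHR-1210; the protocol offers nothing from which to establish or size one.

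**Conclusion.** The overlap is real but minor. For a moderate infusion reaction that recurs after resolution, Table 5 supports both withholding the current infusion and stopping SHR-1210 permanently, with no rule to choose between them. The consequence is inconsistent handling of SHR-1210 and an uncertain split between interruption and discontinuation due to AEs.

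This rests on reading recurrence as an alternative grade 3 descriptor, which the punctuation allows but does not force, and on a site using the reference table. The expected number of affected patients cannot be derived from the protocol and may be zero. No effect on the primary ORR analysis, PFS or duration of response is claimed.

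**What to change.** Edit Table 5 so that recurrence after resolution appears under one grade only, and make that grade agree with the CTCAE v4.03 grade used for recording and for the reporting rules in 8.3 and 9.3. In the same edit, reconcile the table's permanent stop from grade 3 with section 5.3, which names grade 4 only. Which clinical consequence applies, and at which grade, is for the sponsor and investigator to decide; the request is only that the passages agree.

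The cost is a short text change to Table 5 and, if needed, to section 5.3. Sample size, data collection and planned analyses are unaffected.

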9.4. Symptomatic management of apatinib-related adverse reactions

1) Hand and foot syndrome (HFS)

HFS is characterized by palmar-plantar hypoaesthesia or erythema of extremities, which is a type of skin toxicity that becomes more apparent in areas subjected to pressure or force. This can occur in cancer patients receiving chemotherapy or molecular targeted therapy. The features of hand and foot skin reactions (HFSR) include numbness, dysesthesia, paresthesia, tingling sensation, painlessness or pain, skin swelling, erythema, desquamation, rhagades, indurated blisters, and severe pain.

HFS grading:

Grade 1: Numbness/dysesthesia /paresthesia of hands and/or feet, painless swelling or erythema, and/or discomfort not affecting normal activities.

Grade 2: Painful erythema and swelling of the hands and/or feet, and/or discomfort affecting the daily activities of patients.

Grade 3: Wet desquamation, ulcer, blisters, or severe pain of the hands and/or feet, and/or severe discomfort that prevents the patient from working or performing daily activities. Severe pain and loss of skin function are relatively rare.

Symptomatic treatment and management of HFS:

It is recommended to implement some necessary symptomatic supportive treatments, including: enhancing skin care, maintaining skin cleanliness, and avoiding secondary

infections; avoiding pressure or friction; using moisturizers or lubricants, topically applying emulsions or lubricants containing urea and corticosteroids; when necessary, topically using antifungal or antibiotic treatments.

Note: If \geq grade 3 HFS occurs consecutively for 3 times and shows a worsening trend, the study drug will be discontinued and the patient will be withdrawn from the clinical study.

2) Hypertension

For patient enrollment, the inclusion and exclusion criteria regarding blood pressure requirements should be followed strictly. Hypertensive patients can achieve blood pressure control before taking the investigational drug by adjusting the dose of antihypertensive medication or adding a new antihypertensive drug. Blood pressure must be controlled within 140/90 mmHg before randomization (the mean of 2 blood pressure measurements, with a 24-hour or longer interval). Monitoring and management of such hypertension: During the first 2 cycles of targeted drug therapy, blood pressure should be monitored at least 3 times per week.

Since anti-VEGF/VEGFR targeted therapy drugs cause a decrease in NO synthesis, ultimately activating the renin-angiotensin-aldosterone system and leading to hypertension, it is preferable to use angiotensin-converting enzyme (ACE) inhibitors (such as captopril, enalapril, benazepril, and cilazapril) for antihypertensive treatment. For patients who are allergic or intolerant to ACE inhibitors, angiotensin II receptor blockers (ARBs, such as losartan, valsartan, irbesartan, and telmisartan) can be used. In addition to lowering blood pressure, ARBs also have benefits in alleviating proteinuria. ACE inhibitors can be used in patients with chronic kidney disease, proteinuria, and metabolic syndrome; dihydropyridine calcium channel blockers are suitable for elderly patients.

If patients experience hypertension or worsening of hypertension during the treatment, the following actions should be taken: 1) Perform dose modifications of the study drugs according to the protocol requirements; 2) Initiate antihypertensive medication or adjust the dose of antihypertensive medication.

In the study, it is recommended to use the following antihypertensive medications: 1) ACE inhibitors; 2) ARBs; 3) Dihydropyridine calcium channel blockers; 4) β -adrenergic receptor blockers.

It is not recommended to use diuretic antihypertensive drugs, and the use of nifedipine, diltiazem, and verapamil, which have CYP3A4 inhibitory effects, is prohibited during the treatment with the study drugs. For patients with hypertensive crisis, the use of apatinib should be discontinued.

3) Hemorrhage

Haemorrhage of digestive tract, including fecal occult blood (++) or above, hematemesis, or bloody stools, should be actively managed with symptomatic treatment. Patients with upper gastrointestinal haemorrhage should be fasted and given therapies such as acid suppression, gastric mucosal protection, and hemostatic agents (such as tranexamic acid and reptilase). If necessary, octreotide can be used. For patients with lower gastrointestinal haemorrhage, hemostasis, blood transfusion, and supportive care should be provided. For patients with uncontrolled bleeding, surgical assistance is required immediately.

Patients with coughing blood or hemoptysis should be given hemostasis, blood transfusion, and supportive treatment; if bleeding cannot be controlled, surgical assistance is required.

Note: In cases of confirmed hemorrhage brain, \geq grade 2 pulmonary hemorrhage, or \geq grade 3 hemorrhage, the drug must be discontinued immediately, symptomatic

treatment should be provided, and the use of apatinib should be terminated, with the administration of SHR-1210 suspended. After the symptoms have alleviated or disappeared, the use of SHR-1210 will be continued as appropriate.

4) Proteinuria

Throughout the treatment period, closely monitor proteinuria in all patients, and strengthen monitoring for those with a history of hypertension. For patients with proteinuria of ++ to +++ for 2 consecutive times, a 24-hour urine protein measurement is required. For patients with proteinuria of ++++ and above, a 24-hour urine protein measurement is also required.

Note: If nephrotic syndrome occurs, the medication will be permanently discontinued, and the subject will withdraw from this clinical study.

5) Thrombus

In the event of any arterial thrombosis (such as cerebral ischemia, stroke, angina, myocardial infarction), the medication should be stopped immediately, and the subject should withdraw from the study. If symptomatic venous thrombosis (grade 4) occurs, the medication should be stopped, and the subject should withdraw from the study. Thrombosis symptoms should be treated immediately with symptomatic treatment, surgery, or anticoagulants.

6) Fatigue and weakness

Fatigue and weakness are common tumor-related clinical symptoms, and electrolyte disturbance, abnormal liver function, and abnormal cardiac function may lead to fatigue and weakness. In addition, fatigue and weakness are common clinical adverse reactions of angiogenesis-targeting drugs such as sunitinib, pazopanib, and sorafenib. Clinical studies have shown that angiogenesis-targeting drugs may increase the incidence of fatigue and weakness by causing hypothyroidism.

In previously completed clinical studies of apatinib, the incidence of fatigue and weakness in patients in the apatinib treatment group was higher than that in the control group. However, the specific mechanism underlying the increased incidence of fatigue and weakness induced by apatinib is not yet clear.

Therefore, when patients experience or report \geq grade 2 fatigue and weakness, it should be paid more attention to. If \geq grade 3 fatigue and weakness occur, patients should be admitted to the hospital immediately for examination. Potential causes, such as electrolyte disturbance, abnormal liver function, abnormal cardiac function (electrocardiogram, echocardiography), and abnormal hormone levels (adrenal hormones, thyroid hormones), should be considered and ruled out one by one. Symptomatic treatment should be provided, and according to the dose adjustment principles, the dose interruption or adjustment should be performed on the investigational drug accordingly.

7) Abdominal pain

Abdominal pain is not uncommon in apatinib treatment, often as a symptom associated with the tumor. Moreover, gastrointestinal perforation occasionally occurs in clinical studies of apatinib and other types of anti-angiogenic drugs. For patients experiencing abdominal pain, investigators should be vigilant for the possibility of gastrointestinal perforation. Once gastrointestinal perforation is identified, the medication must be stopped immediately, the patient should withdraw from the study, and active symptomatic treatment should be initiated.

8) Pulmonary interstitial fibrosis

Clinical physicians should have a thorough understanding of the patient's disease condition and be familiar with drugs that may cause pulmonary toxicity. The patient's clinical symptoms and changes in chest X-ray or CT scans should be closely

monitored. Once the patient experiences unexplained symptoms such as cough, chest tightness, breathlessness, difficulty breathing, and hemoptysis, it is crucial to promptly identify the cause and discontinue the medication as soon as other causes (such as infection and heart failure) are ruled out.

Bronchoalveolar lavage examination and surgical lung biopsy are important methods for diagnosing interstitial lung disease. Currently, there is no satisfactory treatment for pulmonary fibrosis. It is recommended to refer to the guidelines for the diagnosis and treatment of idiopathic pulmonary (interstitial) fibrosis issued by the Respiratory Diseases Branch of the Chinese Medical Association, correct hypoxemia, and drugs such as glucocorticoids should be used in a timely manner.

Note: Consult with a specialist if necessary to assist in diagnosis and treatment.

10. Data Analysis / Statistical Methods

Screening-failed subjects (those who signs the ICF but do not receive any treatment) will not be included in any analysis. However, these subjects will be reported separately in the form of a list.

